6.0 STATISTICAL CONSIDERATIONS

In this pilot study that aims to investigate the feasibility of applying VRT-DIBH to assist lung/liver cancer SBRT, we will recruit 10 patients. A sample size justification was not made since this is a pilot study to explore the feasibility of using VisionRT guided DIBH. Descriptive statistics will be computed to estimate the sample size needed for a future larger trial if the study results look promising. The trial is considered feasible and promising if 50% of enrolled patients can finish breath-holding SBRT.

6.1 Study Design/Study Endpoints

A single-center prospective pilot study will be conducted according to the schema outlined at the beginning of this document. Informed consent will be obtained from 10 thoracic or abdominal cancer patients, each to be treated with SBRT technique. In order to quantify tumor motion/surface stability and repeatability during VRT-DIBH, several CT images will be acquired during treatment simulation, as well as CBCT and VRT surface images during treatment delivery. The designed study aims to explore the geometry and dosimetry accuracy of VRT-DIBH in thoracic or abdominal cancer SBRT.

6.2 Sample Size and Accrual

As this is a pilot study, we will recruit 10 patients and use descriptive statistics to characterize tumor motion/surface stability & repeatability during VRT-DIBH and its dosimetric impact in terms of dose deviation to tumor and critical organs.

A sample size justification was not made since this is a pilot study. Descriptive statistics will be computed to estimate the sample size needed for a future larger trial if the study results look promising. We anticipate that the proposed trial will be completed in 2 years since at least 5 patients are expected to be recruited a year.

6.3 Data Analyses Plans

All recorded CBCT images will be used for tumor and critical organs geometry accuracy study by exporting to Velocity software. PTV and critical organs will be delineated. Tumor position accuracy will be evaluated. Further delivered dosimetric accuracy will be evaluated with through dose calculation on acquired CBCT images.

7.0 ADVERSE EVENTS

7.1 Adverse Event Monitoring

Adverse event data collection and reporting, which are required as part of every clinical trial, are done to ensure the safety of subjects enrolled in the studies as well as those who will enroll in future studies. Adverse events are assessed in a routine manner at scheduled times during a trial. Additionally, certain adverse events must be reported in an expedited manner to allow for optimal monitoring of subject safety and care.

All subjects experiencing an adverse event, regardless of its relationship to study therapy, will be monitored until:

- the adverse event resolves or the symptoms or signs that constitute the adverse event return to baseline or is stable in the opinion of the investigator;
- there is a satisfactory explanation other than the study therapy for the changes observed; or
- death.

[Inserted from Adverse Event Definitions and Reporting Section – Appendix II of the SCCC DSMC Plan]

7.1.1 **Definitions**

An adverse event is defined as any untoward or unfavorable medical occurrence in a human research study participant, including any abnormal sign (for example, abnormal physical exam, imaging finding or clinically significant laboratory finding), symptom, clinical event, or disease, temporally associated with the subject's participation in the research, whether or not it is considered related to the subject's participation in the research.

Adverse events encompass clinical, physical and psychological harms. Adverse events occur most commonly in the context of biomedical research, although on occasion, they can occur in the context of social and behavioral research. Adverse events may be expected or unexpected.

Acute Adverse Events

Adverse events occurring in the time period from the signing of the informed consent, through **the last day of treatment** will be considered acute adverse events.

Severity

Adverse events will be graded by a numerical score according to the defined NCI Common Terminology Criteria for Adverse Events (NCI CTCAE) Version 5.0. Adverse events not specifically defined in the NCI CTCAE will be scored on the Adverse Event log according to the general guidelines provided by the NCI CTCAE and as outlined below.

- Grade 1: Mild
- Grade 2: Moderate
- Grade 3: Severe or medically significant but not immediately life threatening
- Grade 4: Life threatening consequences
- Grade 5: Death related to the adverse event

Serious Adverse Events

OHRP and UTSW HRPP define serious adverse events as those events, occurring at any dose, which meets any of the following criteria:

- results in death;
- is life-threatening (places the subject at immediate risk of death from the event as it occurred);
- results in inpatient hospitalization^{1,2} or prolongation of existing hospitalization;
- results in a persistent or significant disability/incapacity;
- results in a congenital anomaly/birth defect; or
- based upon appropriate medical judgment, may jeopardize the subject's health and may require medical or surgical intervention to prevent one of the other outcomes listed in this definition.

Note: A "Serious adverse event" is by definition an event that meets **any** of the above criteria. Serious adverse events may or may not be related to the research project. A serious adverse event determination does not require the event to be related to the research. That is, both events completely unrelated to the condition under study and events that are expected in the context of the condition under study may be serious adverse events, independent of relatedness to the study itself. As examples, a car accident requiring ≥ 24 hour inpatient admission to the hospital would be a serious adverse event for any research participant; likewise, in a study investigating end-stage

cancer care, any hospitalization or death which occurs during the protocol-specified period of monitoring for adverse and serious adverse events would be a serious adverse event, even if the event observed is a primary clinical endpoint of the study.

¹Pre-planned hospitalizations or elective surgeries are not considered SAEs. Note: If events occur during a pre-planned hospitalization or surgery, that prolong the existing hospitalization, those events should be evaluated and/or reported as SAEs.

² NCI defines hospitalization for expedited AE reporting purposes as an inpatient hospital stay equal to or greater than 24 hours. Hospitalization is used as an indicator of the seriousness of the adverse event and should only be used for situations where the AE truly fits this definition and NOT for hospitalizations associated with less serious events. For example: a hospital visit where a patient is admitted for observation or minor treatment (e.g. hydration) and released in less than 24 hours. Furthermore, hospitalization for pharmacokinetic sampling is not an AE and therefore is not to be reported either as a routine AE or in an expedited report.

7.1.2 Unanticipated Problems Involving Risks to Subjects or Others (UPIRSOs):

The phrase “unanticipated problems involving risks to subjects or others” is found, but not defined in the HHS regulations at 45 CFR 46, and the FDA regulations at 21 CFR 56.108(b)(1) and 21 CFR 312.66. For device studies, part 812 uses the term unanticipated adverse device effect, which is defined in 21 CFR 812.3(s). Guidance from the regulatory agencies considers unanticipated problems to include any incident, experience, or outcome that meets ALL three (3) of the following criteria:

- Unexpected in terms of nature, severity or frequency given (a) the research procedures that are described in the protocol-related documents, such as the IRB-approved research protocol and informed consent document; and (b) the characteristics of the subject population being studied;
AND
- Related or possibly related to participation in the research (possibly related means there is a reasonable possibility that the incident, experience, or outcome may have been caused by the procedures involved in the research);
AND
- Suggests that the research places subjects or others at greater risk of harm (including physical, psychological, economic, or social harm) than was previously known or recognized. Note: According to OHRP, if the adverse event is serious, it would always suggest a greater risk of harm.

Follow-up

All adverse events will be followed up according to good medical practices.

7.2 Steps to Determine If a Serious Adverse Event Requires Expedited Reporting to the SCCC DSMC

Step 1: Identify the type of adverse event using the NCI Common Terminology Criteria for Adverse Events (CTCAE v5).

Step 2: Grade the adverse event using the NCI CTCAE v5.

Step 3: Determine whether the adverse event is related to the protocol therapy.
Attribution categories are as follows:

- Definite – The AE is *clearly related* to the study treatment.

- Probable – The AE is *likely related* to the study treatment.
- Possible – The AE *may be related* to the study treatment.
- Unlikely – The AE *may NOT be related* to the study treatment.
- Unrelated – The AE is *clearly NOT related* to the study treatment.

Note: This includes all events that occur [to the end of the acute adverse events reporting period as defined in section 7.1.1.](#)

Step 4: Determine the prior experience of the adverse event. Expected events are those that have been previously identified as resulting from administration of the treatment. An adverse event is considered unexpected, for expedited reporting purposes only, when either the type of event or the severity of the event is not listed in:

- the current known adverse events listed in the Agent Information Section of this protocol (if applicable);
- the drug package insert (if applicable);
- the current Investigator's Brochure (if applicable)
- the Study Agent(s)/Therapy(ies) Background and Associated Known Toxicities section of this protocol

7.2.1 Reporting SAEs and UPIRSOs to the Simmons Comprehensive Cancer Center (SCCC) Data Safety Monitoring Committee (DSMC)

SAEs and UPIRSOs at all sites, which occur in research subjects on protocols for which the SCCC is the DSMC of record require reporting to the DSMC regardless of whether IRB reporting is required. All SAEs occurring during the protocol-specified monitoring period and all UPIRSOs should be submitted to the SCCC DSMC within 5 business days of the study team members awareness of the event(s). In addition, for participating centers other than UTSW, local IRB guidance should be followed for local reporting of serious adverse events or unanticipated problems.

The UTSW study PI is responsible for ensuring SAEs/UPIRSOs are submitted to the SCCC DSMC Coordinator. This may be facilitated by the IIT project manager, study team, sub-site or other designee. Hardcopies or electronic versions of the eIRB Reportable Event report; FDA Form #3500A forms, or other sponsor forms, if applicable; and/or any other supporting documentation available should be submitted to the DSMC Coordinator. The DSMC Coordinator forwards the information onto the DSMC Chairman who determines if immediate action is required. Follow-up eIRB reports, and all subsequent SAE or UPIRSO documentation that is available are also submitted to the DSMC Chair who determines if further action is required. (See *Appendix III of the SCCC DSMC Plan for a template Serious Adverse Event Form which may be utilized*).

If the event occurs on a multi-institutional clinical trial coordinated by the UTSW Simmons Comprehensive Cancer Center, the IIT Project Manager or designee ensures that all participating sites are notified of the event and resulting action, according to FDA guidance for expedited reporting. DSMC Chairperson reviews all SAEs and UPIRSOs upon receipt from the DSMC Coordinator. The DSMC Chairperson determines whether action is required and either takes action immediately, convenes a special DSMC session (physical or electronic), or defers the action until a regularly scheduled DSMC meeting.

Written reports to:
(Investigator/study team: Insert names, fax numbers, an addresses for required notifications)

UTSW SCCC Data Safety Monitoring Committee Coordinator Email: [contact] [contact] or deliver to BLB.306
 
UTSW Institutional Review Board (IRB) Submit a Reportable Event via eIRB with a copy of the final sponsor report as attached supporting documentation

--

Reporting Unanticipated Problems Involving Risks to Subjects or Others (UPIRSOs) to the UTSW HRPP

UTSW reportable event guidance applies to all research conducted by or on behalf of UT Southwestern, its affiliates, and investigators, sites, or institutions relying on the UT Southwestern IRB. Additional reporting requirements apply for research relying on a non-UT Southwestern IRB.

According to UTSW HRPP policy, UPIRSOs are incidents, experiences, outcomes, etc. that meet ALL three (3) of the following criteria:

1. Unexpected in nature, frequency, or severity (i.e., generally not expected in a subject's underlying condition or not expected as a risk of the study; therefore, not included in the investigator's brochure, protocol, or informed consent document), AND
2. Probably or definitely related to participation in the research, AND
3. Suggests that the research places subjects or others at a greater risk of harm (including physical, psychological, economic, or social harm) than was previously known or recognized. Note: According to OHRP, if the adverse event is serious, it would always suggest a greater risk of harm.

For purposes of this policy, UPIRSOs include unanticipated adverse device effects (UADEs) and death or serious injury related to a humanitarian use device (HUD).

UPIRSOs must be promptly reported to the UTSW HRPP within 5 working days of study team awareness.

For research relying on a non-UT Southwestern IRB (external, central, or single IRB):

Investigators relying on an external IRB who are conducting research on behalf of UT Southwestern or its affiliates are responsible for submitting LOCAL UPIRSOs to the UT Southwestern IRB within 5 working days of study team awareness. Investigators must report to their relying IRB according to the relying IRB's policy. In addition, the external IRB's responses or determinations on these local events must be submitted to the UT Southwestern IRB within 10 working days of receipt.

Events NOT meeting UPIRSO criteria:

Events that do NOT meet UPIRSO criteria should be tracked, evaluated, summarized, and submitted to the UTSW HRPP/IRB at continuing review.

For more information on UTSW HRPP/IRB reportable event policy, see
<https://www.utsouthwestern.edu/research/hrpp/quality-assurance/>

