4.0 TREATMENT PLAN

4.1 Treatment Dosage and Administration

Patient recruit on this treatment protocol will go through training-screening sessions:

1. Patient will go through a tumor motion evaluation session. Since we would like to test the effectiveness of our proposed motion management strategy, we would like to recruit patient with tumor motion in one direction is larger than 5 mm. Tumor motion in free-breathing mode will be evaluated under imaging study..
2. Patient will go through a pre-oxygenation training-screening session. Research studies^{18, 19} already shown that pre-oxygenation can effectively prolong breath-holds in patients with cancer. In this study we will combine patient training, screening, and pre-oxygenation to prolong patient breath-hold duration in radiotherapy procedure. Patient will be asked to breathing oxygen-enhanced air through a facial mask and take deep inspiration breath hold. We will use spirometer to find the maximum deep inspiration breath level and set a comfortable/optimal breath hold level ~75% of the maximum deep inspiration. Only patient can have single DIBH duration \geq 30 seconds will be eligible for the study.
3. Patient will go through a real-time coaching training session assisted by DIBH technique. After being trained, patient will go through motion assessment section. Patient will be set on treatment couch with chest exposed which allows cameras catch patient body surface information. Spirometer will be used to assist DIBH setup. Optical camera system will be used to acquire patient chest/abdomen surface. During the surface image acquisition, imaging will be used to acquire tumor position or diaphragm position. The surface images and tumor positions acquired in single DIBH durations will be used to quantify intra-DIBH patient surface and tumor position stability. The surface images and tumor positions acquired across several DIBH durations will be used to quantify inter-DIBH patient surface and tumor position repeatability. The intermittent time between DIBH durations can be varied between 1-10 minutes.
4. Only patient with inter/intra-DIBH tumor position variation \leq 5 mm and inter/intra-DIBH surface level variation \leq 5 mm will be move on for this VRT-DIBH protocol study. Otherwise, patients will be off study and treated per standard of care.

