4.4 Duration of Follow Up

No follow-up required for this study after radiation completed.

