5.0 STUDY PROCEDURES**5.1 Screening/Baseline Procedures**

Assessments performed exclusively to determine eligibility for this study will be done only after obtaining informed consent. Assessments performed for clinical indications (not exclusively to determine study eligibility) may be used for baseline values even if the studies were done before informed consent was obtained.

All screening procedures must be performed within 60 days prior to registration unless otherwise stated. The screening procedures include:

5.1.1 *Informed Consent***5.1.2 *Medical Diagnosis*****5.1.3 *Demographics***

Age

5.1.4 *Review subject eligibility criteria***5.1.5 *Physical exam including vital signs, height and weight***

Vital signs (temperature, pulse, respirations, blood pressure) for each protocol related visit.

5.1.6 *Adverse event assessment*

None

5.1.7 *Pregnancy test (for females of child bearing potential)*

See section 3.1.3 for definition. This is done prior to enrollment. Patients may refuse testing if they attest they are not pregnant.

5.1.8 *Breathing evaluation*

Treatment target motion, surface motion and breathing duration will be evaluated before SBRT (does not have to be done prior to registration). The following screening procedures will be pursued sequentially:

1. Free-breathing tumor motion evaluation: imaging will be acquired and physician will determine whether tumor motion > 5 mm.
2. For those patients with tumor motion > 5 mm, breath-holding duration will be evaluated. At this stage, patient will be positioned supine in a stable position. Patient will be asked to breathe oxygen-enhanced air and then take deep inspiration breath hold. Ask patient to repeat breath-holding 3 times and record breath-holding time. If patients can hold breath ≥ 30 seconds in all three times, patients will be eligible for the study.

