3. Patient will be monitored by optical cameras to assess surface motion. Air tube will be setup to assist oxygen-enhanced air breathing. ***Care must be taken to ensure tubing is not over patient chest, as optical cameras will acquire surface images for motion evaluation.*** Patient will be instructed to conduct DIBH and optical cameras will monitor patient surface during breath hold. If surface motion > 5 mm during the breath hold, patient will not be qualified for this trial. Another test is that we will instruct patient to repeat breath hold three times. If patient is able to repeat breath hold to the level of the first setting within 5 mm tolerance, patient will move on for the further study step.
4. DIBH tumor motion evaluation: after surface motion evaluation, DIBH tumor motion evaluation will be conducted under imaging one more time. Imaging will be acquired and physician will determine whether tumor motion ≤ 5 mm in one direction.

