5.4 Time and Events Table

	Pre-study	Treatment
Assessment		
Informed Consent	X	
History and PE ^A	X	X ^C
Pregnancy Test ^B	X	
CBCT scans		X

^A include vital signs

^B Recommended but patient may refuse if they attest they are not pregnant

^C Only vital signs, once per week

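### Does the lack of a named visit for adverse event assessment require a change to the protocol?

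*Combined protocol and SAP*

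**What the plan says.** The general statement is in Section 7.1: "Adverse events are assessed in a routine manner at scheduled times during a trial". Section 7.1.1 defines acute events by a window: "Adverse events occurring in the time period from the signing of the informed consent, through" the final treatment day.

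Section 5 is where a reader would look for the times.

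- Section 5.1.6 is headed "Adverse event assessment", and the only entry beneath it is None.
- Section 5.1.5 asks for "Vital signs (temperature, pulse, respirations, blood pressure) for each protocol related visit".
- Section 5.1.8 sets four sequential steps (free-breathing motion, breath-hold duration, surface motion, tumor motion in breath-hold) and mentions AEs in none of them.
- Section 5.2 covers simulation, contouring, planning, daily treatment and later analysis, and does not mention AEs.
- Table 5.4 has four rows (consent, history and examination, pregnancy test, CBCT). Its footnote for the examination during treatment reads "Only vital signs, once per week".

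On leaving the study, Section 4.1 says of patients who miss the motion limits: "Otherwise, patients will be off study and treated per standard of care". Section 5.1.8 says: "If surface motion > 5 mm during the breath hold, patient will not be qualified for this trial". Section 4.4 adds: "No follow-up required for this study after radiation completed".

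**The concern.** Read together, these sections look like a promise without a timetable. Section 7.1 speaks of scheduled times, and the one item in Section 5 that carries the right heading is filled in with None. Someone who worked only from Section 5 would never be told to ask a patient about AEs.

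The gap also falls at an awkward point. After consent, patients breathe oxygen-enhanced air and must hold their breath for at least 30 seconds on three occasions. Further breath-holds follow for the surface and tumor-motion tests. Three of the four steps in 5.1.8 (duration, surface motion, tumor motion in breath-hold) involve a breath-hold and can end participation. A patient who fails one leaves with no later study visit.

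At stake is the recording of non-serious events from these research procedures. If they are noted only when staff happen to see them or the patient mentions them, the AE data that the monitoring committee reviews each quarter (Section 8.4) could be incomplete, most of all for patients who leave early.

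**Working it through.** The plan states no figure here, so there is nothing to recompute. The check has three parts.

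**1. Is an AE time point named anywhere?**

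| Place | Items | Items naming an AE check |
|---|---|---|
| 5.1.6 | 1 | 0 (entry is None) |
| 5.1.8 | 4 steps | 0 |
| 5.2 | 6 headings, of which 2 (5.2.1, 5.2.5) involve patient contact | 0 |
| 5.3 | no study follow-up | 0 |
| 5.4 | 4 rows | 0 |

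No time point is named. These rows should not be added into one fraction. Four of the six headings in 5.2 are desk work, and the consent, pregnancy-test and CBCT rows of the table would never hold an AE check. The table is also not a full list of procedures: it omits the breathing evaluation and CT simulation. The numbering in 5.2 jumps from 5.2.5 to 5.2.8, and the document as supplied has no 5.2.6 or 5.2.7.

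**2. Do the sections contradict each other?**

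- The sentence in 7.1 refers to *a trial*, and the sentence before it is about every clinical trial. It describes general practice and gives no study-specific interval.
- Item 5.1.6 belongs to Screening/Baseline Procedures. There, None most plausibly means that no pre-existing events are recorded as a baseline. That is compatible with a window that opens at consent.
- So one general statement has not been turned into visit times. There are not two schedules that disagree.

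**3. What does the plan do with AEs once the window is open, and which results use them?**

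Handling:

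- 7.1 requires every subject with an AE to be monitored until it resolves, stabilizes or is otherwise explained, or until death. Patients who fail a breath-hold test are not exempted.
- 7.1.1 requires CTCAE version 5.0 grading and refers to an AE log.
- 7.2.1 requires serious events and unanticipated problems to reach the monitoring committee within 5 business days.
- Section 7.2 also requires events that are not unanticipated problems to be tracked and summarized for the review board at continuing review.
- 8.4 provides quarterly committee review of AEs.

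Use:

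- The endpoints in 2.4 are feasibility, target margin and surface threshold. AEs are not among them.
- The analysis plan in 6.3 covers geometry and dose on CBCT images.
- Section 6.0 calls the trial feasible if 50% of enrolled patients finish. With the planned enrollment that is 0.50 × 10 = 5 patients, and an AE count does not enter.
- 7.4 gives no stopping rule, so no threshold depends on a complete count.

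A missed non-serious event would therefore leave the planned estimates and the feasibility criterion unchanged.

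**The case for a change.** The best case for a change is that Section 7 deals with events already known, whereas the gap is in finding them. Vital signs do not elicit symptoms or psychological harms, both of which fall within the AE definition in 7.1.1. Quarterly committee review looks at data already collected. Section 8.5 requires the study to be run exactly as the protocol describes, and Section 5 taken literally describes no AE check. Section 4.5 says that removed subjects are followed per protocol, yet the protocol sets no follow-up. With only 10 patients and no stopping rule, a few missed events could alter the safety picture, and the remedy would be cheap: a table row and a clarified entry.

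Much of this stands as a comment on drafting. The protocol does not say when staff ask about events, and a reader has to infer what None means. It does not amount to a defect in the plan. Section 7 is as much part of the approved protocol as Section 5, and it places AE collection from consent onward on the study team. The breath-hold sessions are staff-run: patients are instructed, their breath-holds are timed, and cameras monitor the body surface. Acute events there would occur in front of the people who keep the log. Patients who fail a test go on to standard care. Case report forms and a study-specific monitoring plan exist (Section 8.4) but were not supplied, and they are the usual place for visit-level prompts.

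**Conclusion.** The factual point is right: no visit for an AE assessment is named. No change follows, because this is missing operational detail that staff fill sensibly under Section 7. No stated rule gives a wrong result, and no endpoint, planned analysis or feasibility decision depends on the AE count. Serious events and unanticipated problems are fully covered.

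What remains is possible under-recording of non-serious events around the breath-hold sessions. Its size cannot be estimated from the documents.

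The conclusion rests on three assumptions: that None in 5.1.6 concerns baseline only, that staff at the breath-hold and treatment sessions log the events they see or are told of, and that the case report forms or monitoring plan contain nothing to the contrary. If AE rates were later reported as a result of the study, or if None were meant to switch off collection between consent and treatment, the point would carry more weight.
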